## 9 STATISTICAL CONSIDERATIONS

## 9.1 STATISTICAL HYPOTHESES

Primary Endpoint:

- Overdose Admissions
  - [Measured: 1 year pre-enrollment through 1 year post-enrollment]

We hypothesize that, compared to patients in the control condition, patients receiving the POINT intervention will experience fewer subsequent admissions to the ED for overdose.

Secondary Endpoints:

- MOUD Engagement
  - [Measured: 1 year pre-enrollment through 1 year post-enrollment]
- Duration of MOUD Engagement
  - [Measured: 1 year pre-enrollment through 1 year post-enrollment]
- ED Admissions
  - [Measured: 1 year pre-enrollment through 1 year post-enrollment]
- Inpatient Hospital Admissions
  - [Measured: 1 year pre-enrollment through 1 year post-enrollment]
- Time to Relapse
  - [Measured: Enrollment through 1 year post-enrollment]
- Medicaid Enrollment for Participants Without Insurance
  - [Measured: Enrollment through 1 year post-enrollment]
- Child Welfare Involvement
  - [Measured: 3 years pre-enrollment through 1 year post-enrollment]
- Incarceration
  - [Measured: 3 years pre-enrollment through 1 year post-enrollment]

We hypothesize that, compared to patients in the control condition, patients receiving the POINT intervention will experience better recovery outcomes (i.e., higher MOUD engagement and longer duration of engagement, lower ED and inpatient admissions, longer times between relapse, higher Medicaid enrollment for those without insurance, lower child welfare involvement, and lower incarceration).

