### 9.4 STATISTICAL ANALYSES

#### 9.4.1 GENERAL APPROACH

We will summarize patient characteristics using means and standard deviations for continuous variables and counts and proportions for categorical variables. Initial analysis of outcomes (using data pulled at 9 months) will focus on MOUD engagement one-month post overdose, as all other outcomes will be too distal to observe any meaningful change. This time period is based on our prior POINT experience demonstrating initial engagement tends to happen within 1-2 weeks of overdose. We will focus on immediate outcomes (e.g., treatment engagement, length, dropout). While observed change in more distal outcomes (e.g., subsequent overdose and mortality) is unlikely to be seen in such a short pilot period, we will look at them and, if needed, adjust the benchmark (established based on our experience at Eskenazi) for the power analysis. Summary of outcome measures will be computed similarly. The 95% confidence intervals of outcome measures for the POINT and standard care arms will be used to estimate the rate of binary outcomes and mean of continuous outcomes.

The primary analysis involves comparison of outcome measures post ED discharge between the POINT and standard care arms. Binary outcome measures (e.g., MOUD engagement and dropout, subsequent overdose, overdose mortality, and all-cause mortality) will be compared between the POINT and standard care arms using the Fisher's exact test. Length of MOUD treatment will be compared using the Wilcoxon rank sum test. Comparison of the length of time to relapse will be conducted using the survival analysis. Time to relapse will be plotted using the Kaplan Meier curve and comparison between the POINT and standard care arms will be performed using the log rank test.

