The secondary analysis involves comparing outcome measures pre- and post-ED discharge for POINT patients. Binary outcomes including child welfare involvement will be compared using the McNemar's test and the continuous outcome including the days of incarceration will be compared using the Wilcoxon signed rank test due to the skewness of the data. Additional analyses will be conducted to account for patient characteristics in the comparison between the POINT and standard care arms using logistic regression for binary outcomes, Poisson regression for length of MOUD treatment, and Cox proportional hazards model for time to relapse. For the comparison pre- and post-ED discharge in the POINT arm, generalized estimating equations approach will be performed using logistic regression for Medicaid enrollment and child welfare involvement and Poisson regression for days of incarceration. Hospitals will be included in the models as a fixed effect to account for the potential differences in patient population across hospitals.

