#### 9.4.3 ANALYSIS OF THE SECONDARY ENDPOINT(S)

Secondary endpoints	
Note if analysis of secondary endpoint(s) are dependent on findings of primary endpoint	Analysis of secondary endpoints are not dependent on the findings of primary endpoint.
Describe how each secondary endpoint is calculated, if not readily apparent	
Change in MOUD Engagement: Using state methadone treatment data, Medicaid claims data, state prescription drug monitoring data, and electronic health records data to identify whether or not the person engaged in at least one episode of MOUD treatment (methadone, buprenorphine, or naltrexone) within the specified time period.
 
Change in MOUD Engagement Duration: Using state methadone treatment data, Medicaid claims data, state prescription drug monitoring data, and electronic health records data to calculate the number of days MOUD treatment was received during the specified time period.
 
Change in ED Admissions: Using electronic health records, it is calculated as the total combined number of all-cause ED presentation within the specified time period.
 
Change in Inpatient Hospital Admissions: Using electronic health records, it is calculated as the total combined number of all-cause hospital admissions within the specified time period.
 
Time to Relapse: Using electronic health records data, it is calculated as number of days to the first overdose ED visit or overdose death since the index ED. Subjects who did not experience overdose ED or overdose death are censored at the end of the specified time period or the time of death due to other reasons, whichever occurred first
 
Change in Medicaid Enrollment for Participants Without Insurance: Using Medicaid claims data to identify Medicaid coverage among participants within the specific time period.

	
Change in Child Welfare Involvement: Using child welfare data to identify the number of new cases and children removed from the home within the specified time period.
 
Change in Incarceration: Using public incarceration data to identify the number of days of incarceration within the specific time period.

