Describe details to check assumptions required for certain types of analyses (e.g., checks on assumptions of normality, transformations or, when appropriate, nonparametric tests)	Nonparametric tests are used to compare endpoints between treatment arms. Fisher's exact test is used for binary variables, Wilcoxon rank sum test is used for continuous variables, and log-rank test is used for time to event variables.
Describe the Populations for which the analysis will be conducted as discussed in Section 9.3, Populations for Analyses	All study participants
Describe how missing data will be handled (e.g., type of imputation technique, if any, and provide justification), and approach to handling outliers, non-adherence and lost to follow-up	We do not expect there to be missing data due to the use of administrative datasets.
If there is more than one primary endpoint or more than one analysis of a particular endpoint, state the statistical adjustment used for Type I error criteria or give reasons why it was considered unnecessary	Not relevant as there is only one primary endpoint and each endpoint is analyzed once.

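### The POINT-only pre/post comparison of child welfare and incarceration, read literally, sets 3 years before enrollment against 1 year after, with no exposure adjustment, so it shows about a threefold fall when nothing has changed

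*Combined protocol and SAP*

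**What the plan says.** Section 9.1 attaches one time frame to both child welfare involvement and incarceration: "Measured: 3 years pre-enrollment through 1 year post-enrollment". Overdose admissions, MOUD engagement and duration, ED admissions and inpatient admissions have 1 year on each side.

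Section 9.4.3 defines the two variables as amounts accumulated over the period. For child welfare: "Using child welfare data to identify the number of new cases and children removed from the home within the specified time period". For incarceration: "Using public incarceration data to identify the number of days of incarceration within the specific time period". Its scale row then makes child welfare binary.

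Section 9.4.1 sets out two layers of analysis. The first is randomised: "The primary analysis involves comparison of outcome measures post ED discharge between the POINT and standard care arms". The second is within one arm: "The secondary analysis involves comparing outcome measures pre- and post-ED discharge for POINT patients". For that second layer, "Binary outcomes including child welfare involvement will be compared using the McNemar's test", days of incarceration are compared by the Wilcoxon signed rank test, and a "generalized estimating equations approach will be performed using logistic regression for Medicaid enrollment and child welfare involvement and Poisson regression for days of incarceration".

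No section gives a separate pre-enrollment window for these tests, equal windows, a per-year scale or a person-time offset.

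**The concern.** A paired pre/post test assumes that the two members of the pair are measured over comparable exposure. Here the only window in the plan is three times as long before enrollment as after it. A person whose yearly risk never changes has three times the opportunity to be counted before enrollment, so the tests return a reduction produced by window length.

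Section 9.1 hypothesises lower child welfare involvement and lower incarceration with POINT. A spurious within-arm fall in exactly these two endpoints could be read as support. A smaller sample makes the artefact less likely to reach significance but does not make it smaller.

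There is a related mismatch for Medicaid enrollment. Section 9.4.1 plans a pre/post GEE for it, but Section 9.1 starts its window at enrollment, so no pre period is defined.

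**Working it through.** **The plan's own figure.** Section 9.2 gives no calculation for the pre/post analysis. Its one calculated figure, 356 per arm for 12% against 6% at 80% power and 5% significance, reproduces (two-sided, pooled variance, no continuity correction: 356; power 0.800). It is used below only as the planned number of POINT patients. Enrollment fell short and the achieved number is not given, so smaller values are shown too.

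**Inputs from the plan.** Pre window 3 years (3 × 365 = 1,095 days), post window 1 year (365 days); the tests named in Section 9.4.1.

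**Assumed inputs, because the plan gives none.** Annual probability of any child welfare involvement: 1%, 3%, 5%, 10%. Incarceration: 3% or 10% yearly chance of a spell, mean spell 45 days. No true change in any person's rate.

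**Incarceration days.** Expected days are proportional to exposure, so pre/post = 1,095/365 = 3.0 before capping at window length. A Poisson model without an offset gives a post/pre ratio of about 1/3 = 0.33.

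**Child welfare, any versus none.** For a person with constant annual rate *l*:

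- P(pre yes, post no) = (1 − e^(−3l)) e^(−l)
- P(pre no, post yes) = (1 − e^(−l)) e^(−3l)
- Ratio = (e^(3l) − 1)/(e^l − 1) = 1 + e^l + e^(2l), which exceeds 3 for every *l* > 0

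Example at 10% a year: pre = 1 − 0.9³ = 27.1%, post = 10%. Discordant cells are 0.271 × 0.9 = 0.244 and 0.1 × 0.729 = 0.073, a ratio of 3.35. If rates vary between people (gamma, shape 0.5), S(t) = (1 + θt)^(−0.5) with θ = 0.9^(−2) − 1 = 0.235. The cells are then S(1) − S(4) = 0.182 and S(3) − S(4) = 0.048, a ratio of 3.8. At 1% a year with a common rate the ratio is 1 + 1/0.99 + 1/0.99² = 3.03.

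**False improvement by exact McNemar** (two-sided 5%, counted only when it favours improvement; ranges span the common-rate and varying-rate models):

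| POINT patients | 1% a year | 3% | 5% | 10% |
|---|---|---|---|---|
| 50 | 0.2% | 7-9% | 19-22% | 41-50% |
| 100 | 3% | 27-30% | 48-53% | 77-84% |
| 200 | 16-17% | 60-62% | 82-86% | 98-99% |
| 356 | 37-38% | 87-89% | 98-99% | 100% |

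With equal 12-month windows the figure is at most 1.9% in every cell.

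**False improvement by signed rank** (1,000 simulated trials per cell; rates vary between people as above; exponential spell lengths; zero differences dropped):

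| Yearly chance | Mean days, pre vs post | n=50 | n=100 | n=356 |
|---|---|---|---|---|
| 3% | 4 vs 1.4 | 9% | 30% | 81% |
| 10% | 16 vs 5 | 48% | 78% | >99% |

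Equal windows give 0-3%. Dividing the 3-year total by 3 equalises the means but still leaves 8-60% false improvement (yearly chance 3-20%, n = 50 to 356). Signed rank responds to how many people have a positive difference, and three years still catches more people with at least one spell than one year does.

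These rates depend on the assumptions. With more frequent and longer spells (0.3 a year, mean 60 days), signed rank rejects in 84%, 99% and 100% of trials at n = 50, 100 and 356.

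**The case against.** The strongest reply is that the defect comes from joining two sections. Section 9.1 gives a measurement span and Section 9.4.1 names tests; neither says that the whole 3-year block forms one side of the pair, and the team may have intended matched periods. That is possible, which is why the point is framed as a literal reading. But this span is the only one the plan supplies, and other endpoints were given 1 year on each side, so a programmer following the text would use 3 years against 1.

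Other points bear on weight:

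- Section 3 classes these two endpoints as exploratory, although the synopsis and Section 9.1 list them as secondary.
- Section 9.4.3 describes only between-arm tests ("Nonparametric tests are used to compare endpoints between treatment arms") and says each endpoint is analysed once, which sits badly with a further POINT-only test in Section 9.4.1. It does not withdraw that test.
- The hypotheses in Section 9.1 are framed against the control condition, so a within-arm change does not formally test them.
- Threefold is exact for days and counts and a floor for McNemar discordant pairs, but the ratio of reported child welfare percentages is smaller: 2.3 to 3.0 at annual risks of 1% to 10%, and about 2 at 20% with strong variation between people.
- The rejection rates rest on assumed inputs; only the 3:1 exposure ratio comes from the plan.

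These points limit the consequences. None removes the unequal exposure.

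**Conclusion.** The concern holds. As written, the POINT-only pre/post analysis of child welfare involvement and incarceration is biased towards improvement by window length: a factor of 3 for days and counts, and 3.0 to 3.8 for discordant pairs at assumed annual risks of 1% to 10%. That size does not depend on the sample. Whether it reaches significance does: under the assumed rates, McNemar false improvement runs from 0.2% (50 patients, 1% a year) to 100% (356 patients, 10% a year).

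The scope is limited. The primary endpoint, the randomised post-discharge comparison, and pre/post comparisons of endpoints with 1 year on each side are unaffected. This should be fixed, but it does not threaten the trial's main conclusion. The conclusion rests on reading the Section 9.1 span as the analysis window; the separate Medicaid mismatch does not depend on that reading.

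**What to change.** 1. In Sections 9.1 and 9.4.1, state equal 12-month pre and post windows for McNemar, signed rank and both GEE models of these two endpoints.
2. Keep the 3-year history, if wanted, as a covariate in the between-arm model, or in the Poisson model with a log person-time offset. Among the planned methods an offset helps only the Poisson model; neither an offset nor per-year scaling repairs McNemar or signed rank.
3. Label the POINT-only pre/post result descriptive. Even with equal windows it cannot separate POINT from regression to the mean after a crisis visit. Draw effect conclusions from the between-arm comparison already planned.
4. For Medicaid enrollment, either state a pre window in Section 9.1 or remove the pre/post GEE from Section 9.4.1.
5. Section 9.2 says the planned analyses have been carried out. State which windows were used, and re-run any pre/post result that used unequal ones.

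The cost is wording, plus any re-run. Section 8.1 already collects 3 years of records before enrollment and 2 years after, so no new data are needed. The downside is that fewer pre-period events are counted. Matched 24-month windows would keep more of them, but would require changing the post window in Section 9.1.

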## 6.3 MEASURES TO MINIMIZE BIAS: RANDOMIZATION AND BLINDING

The study is randomized at the enrollment shift level. Each day of study enrollment is broken into three shifts (8am-3:59pm, 4pm-11:59pm, 12am-7:59am). In advance, each shift is randomly assigned to one of the two enrollment arms (i.e., POINT or control) to determine whether patients discharged during these times will enroll into the POINT arm or the standard care arm. Any individual who is cleared for discharge from the ED for an overdose or for an opioid-related health issue, including opioid withdrawal, abscess (from IV drug use) or active opioid intoxication will be eligible for the study. As determined by the preset randomization, recovery coaches (RC) will engage with patients cleared for discharged from the ED during the POINT shifts and research assistants (RA) will engage with patients cleared for discharged from the ED during control shifts.

Additional note: The study sites plan to implement Project POINT regardless of the research study. We are not modifying any aspect of POINT for the study purposes. Therefore, all recovery coach duties

(baseline administrative data collection, provision of naloxone, patient follow-up) are part of POINT prescribed services that would be carried out regardless of the research. We are randomizing the shift POINT is delivered on to take advantage of the fact that they are not able to fully staff all hospital shifts with a recovery coach--thus allowing us to test the intervention's effectiveness. Only those patients in the standard care arm will be asked to complete data collection activities that would not be completed outside of the research study.

Sample randomization for week of services								
Week	Shift	Day						
		Mon	Tue	Wed	Thu	Fri	Sat	Sun
1	8am-3:59pm	RC	RA	RA	RC	RC	RC	RA
	4pm-11:59am	RA	RC	RC	RA	RA	RA	RC
	12am-7:59am	RC	RA	RA	RC	RA	RA	RC

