### 9.3 POPULATIONS FOR ANALYSES

All participants consented to the trial will be included in the analyses.

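### Adjusted comparison of MOUD days uses plain Poisson regression with no robust variance or dispersion term, so default standard errors would be several times too small

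*Combined protocol and SAP*

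**What the plan says.** Section 9.4.3 defines the duration endpoint from linked administrative records, which are used to "calculate the number of days MOUD treatment was received during the specified time period". Section 9.1 gives the window as "1 year pre-enrollment through 1 year post-enrollment". Section 9.3 sets the population: "All participants consented to the trial will be included in the analyses".

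Two between-arm analyses of this endpoint appear in section 9.4.1. The main one is nonparametric: "Length of MOUD treatment will be compared using the Wilcoxon rank sum test". The other is listed as additional and adjusts for covariates. Its models are given as follows: "logistic regression for binary outcomes, Poisson regression for length of MOUD treatment, and Cox proportional hazards model for time to relapse". The only further modelling detail is a fixed effect for hospital.

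No section names a robust variance, a scale parameter or an overdispersion check. The assumption-check row in section 9.4.3 covers only the nonparametric tests. Generalized estimating equations (GEE) are named only for the pre/post comparison within the POINT arm, which includes "Poisson regression for days of incarceration", so they do not cover the between-arm MOUD model.

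**The concern.** A Poisson model's default standard errors are right only if the variance equals the mean. Days on treatment are not independent rare events: one decision to start and stay produces a long run of days. Non-starters at 0 and starters spread over weeks or months push the variance far above the mean. Section 9.4.1 recognises skewness for days of incarceration, but the MOUD model makes no provision for it.

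This is the only adjusted between-arm analysis planned for MOUD duration, and section 4.1 hypothesises that POINT patients stay in treatment longer. Different staff recruit in the two arms (section 6.3), so baseline imbalance is plausible and readers may lean on the adjusted result. With default errors, that result could look decisive while the Wilcoxon test shows nothing, and no rule says which prevails.

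**Working it through.** **The plan's own figure.** The documents give no figure for the Poisson model. The one calculation that can be reproduced is the sample size in section 9.2 (12% versus 6%, 80% power, 5% level, taken as two-sided):

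n = [1.96·√(2·0.09·0.91) + 0.8416·√(0.12·0.88 + 0.06·0.94)]² / 0.06² = 355.9, so 356 per arm. This matches the plan and is not affected by the concern.

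**Inputs for the check.** From the documents: days in a one-year post-enrollment window, all consented participants, 356 planned per arm. Assumed: the proportion engaged q, the mean m and coefficient of variation cv of days among those engaged, and 100 per arm as a smaller trial, since the enrollment target was not met.

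**Formula.** With zeros for the non-engaged, mean = q·m and variance = q·m²·cv² + q(1−q)·m². Therefore

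φ = variance/mean = m(cv² + 1 − q).

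The true standard error is √φ times the default Poisson one, whatever the sample size. A nominal 5% test then has type I error of about 2·[1 − Φ(1.96/√φ)].

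**Numbers for stays uniform on 1 to L days** (m = (L+1)/2, variance = (L²−1)/12):

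| Stays | m | cv² | q | φ | √φ | Type I error |
|---|---|---|---|---|---|---|
| 1-365 | 183 | 0.332 | 1.0 | 60.7 | 7.8 | 80% |
| 1-365 | 183 | 0.332 | 0.2 | 207.1 | 14.4 | 89% |
| 1-90 | 45.5 | 0.326 | 1.0 | 14.8 | 3.9 | 61% |
| 1-90 | 45.5 | 0.326 | 0.2 | 51.2 | 7.2 | 78% |
| 1-30 | 15.5 | 0.312 | 1.0 | 4.8 | 2.2 | 37% |
| 1-30 | 15.5 | 0.312 | 0.2 | 17.2 | 4.2 | 64% |

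Over a wider grid (q 0.1-0.9, m 14-180, cv 0-1), √φ runs from 1.2 to 18.5. The low end needs 90% engaged, all for an identical 14 days: φ = 14·(0 + 1 − 0.9) = 1.4.

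**Simulation under no arm effect** (2,000 trials per scenario, 100 and 356 per arm, 20/40/60/100% engaged; the long-stay row also includes exponential stays with mean 100 capped at 365):

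| Stays | Default SE too small by | Default Poisson rejects | Poisson significant, Wilcoxon not |
|---|---|---|---|
| Spread over months | 7.8-14.4 | 80-90% | 74-85% |
| 1-90 days | 3.8-7.1 | 61-79% | 55-75% |
| 1-30 days | 2.2-4.1 | 38-64% | 32-59% |

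In the same trials robust errors rejected in 4.3-6.0% and Wilcoxon in 3.9-6.5%. The last column comes from a separate run of the same size.

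**Does covariate adjustment absorb the excess variance?** Barely. With hospital and a strong predictor in the model (prior MOUD, odds ratio about 6; 20-60% engaged; 1,500 trials per scenario), default errors were still 3.3-13.5 times too small and rejected in 54-89%. Robust errors gave 3.9-6.3%, and robust errors clustered on shift 4.5-6.7%.

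**A second data-generating model** (beta-distributed stays, hospital-adjusted, 1,000 trials per scenario) agrees: 60-88% with default errors, against 3.8-6.6% with robust or Pearson-scaled errors.

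**Negative binomial as a replacement** (600 trials per scenario): with 20-60% engaged, model-based standard errors were 1.6-2.3 times too large and rejection was 0-0.3%. With 100% engaged, rejection was 1.0-4.8%.

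**The case against.** The strongest reply is that this is an omission, not a stated error. Section 9.4.1 lists logistic, Poisson and Cox models at the same level of detail and gives a variance estimator for none of them. A Poisson model with sandwich or scaled errors would comply with the text. That is true, but an analyst who follows the text and accepts ordinary defaults gets wrong standard errors.

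Second, the endpoint-specific section 9.4.3 does not mention the Poisson model. It lists Fisher, Wilcoxon and log-rank tests, says each endpoint is analyzed once, and presents continuous endpoints as means or medians. This limits the impact, since the model is supplementary and no section promises its confidence interval. It does not remove the analysis that section 9.4.1 commits to.

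Third, the magnitude is wholly assumed, and reading the outcome as 0 to about 365 post-enrollment days is an interpretation: section 9.1 spans a year either side of enrollment, and section 9.4.3 labels the endpoint a change. Both points stand. The post-enrollment reading follows section 9.4.1, which compares outcomes after ED discharge. The direction is secure; the exact factor is not.

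Fourth, GEE normally comes with empirical standard errors, so no defect is shown in the incarceration model. That also stands, and the suggestion there is only a clarification.

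**Conclusion.** The concern holds. The plan names plain Poisson regression for a zero-heavy count of days and provides nothing for overdispersion. If default standard errors are used, they would be about 2 to 14 times too small across the simulated distributions, and a nominal 5% test would reject in 38-90% of trials with no true difference. These figures depend on assumed engagement rates and lengths of stay. The problem becomes small only if nearly everyone engages for almost identical short stays. Missing the enrollment target does not ease it, because the factor does not depend on sample size.

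The damage is confined to an additional analysis of one secondary endpoint. The primary endpoint, the sample size and the Wilcoxon test of MOUD days are untouched. It should be fixed, but it does not threaten the trial's main result.

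**What to change.** In section 9.4.1, specify log-link (Poisson) regression with robust (sandwich) standard errors for length of MOUD treatment. Clustering on shift is preferable because section 6.3 states "The study is randomized at the enrollment shift level". In simulations with a shift effect (logit SD 0.7, about 2 patients per shift, 100 per arm) this changed little: 4.8-7.3% without clustering and 4.5-7.1% with it. Pearson-scaled errors also controlled type I error in the runs that tried them. A model-based negative binomial is not a good substitute, because it was strongly conservative wherever many participants had zero days. For the GEE on days of incarceration, a few words stating that empirical standard errors are used would suffice.

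The cost is one sentence and one software option. Confidence intervals will be wider, and with few engaged patients in a small sample robust errors can be slightly anticonservative (up to about 7% at 100 per arm). Since section 9.2 describes the planned analyses as already conducted, the sponsor should state which standard errors were used, recompute any adjusted MOUD-duration interval that used the defaults, and report this as a change made after the fact.
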